9.2.2 Assessment of secondary outcomes

The secondary outcomes include each part of the DOOR outcome separately as described in chapter 9.2.1 *Assessment of primary outcome* and time to death up to day 90.

Further secondary outcomes will be assessed as follows:

Clinical outcomes:

- Time to being discharged alive (assessed until day 90)

In the eCRF, we collect the day of hospital discharge (see 5.1 *Primary Outcome* for detailed definition of primary outcome). For participants who die during the hospitalisation, 90 days will be recorded.
- Number of days without being on the Intensive Care Unit (ICU) up to day 90 (i.e. mean number of days being alive without being on the ICU between randomisation until day 90).

After day 90 we will collect from the hospital information system data how many days the participant spent on the ICU. Together with the available data on mortality, we will calculate the "Number of days without being on the ICU".

Infection dynamics and control:

Information on these outcomes is collected from the hospital information system data.

- Persistent bacteraemia: positive blood culture on day 5 (± 1 day) after randomisation. If blood culture on day 2 or 3 is negative, then day 5 blood culture will be assumed to be negative (in case it is not carried out).
- Two or more systemic inflammatory response syndrome (SIRS) criteria on day 5 after randomisation. This includes: 1. Abnormal body temperature ($<36^{\circ}\text{C}$ or $>38^{\circ}\text{C}$), 2. tachypnoea or mechanical ventilation (RR >20 breaths per minute), 3. tachycardia (HR >90 beats per minute in an adult), 4. abnormal leukocyte count (from routine blood sampling on day 5 ± 1 day, defined as $>12.0 \times 10^9/\text{L}$ or $<4.0 \times 10^9/\text{L}$ or $>10\%$ of immature (band) forms).
- Change in C-reactive protein (CRP) from randomisation until day 5 (± 1 day). Day 1 CRP means any blood CRP measurement taken on randomisation day 1 or the calendar day prior to randomisation. If there is more than one measurement, the value recorded is the one taken closest before randomisation.
- Early clinical treatment failure between 5 and 13 days after randomisation leading to treatment change. Newly identified focus of *S. aureus* between 14 and 90 days after randomisation as determined by the site investigator. This can incorporate clinical, radiological, microbiological, and pathological findings.
- Early microbiological treatment failure between 5 and 13 days after randomisation leading to treatment change. Any positive sterile site culture with *S. aureus* between 5 and 13 days after randomisation. A sterile site means any site of the body where microorganisms are usually absent, i.e. below the outer and inner colonised surfaces of the skin and mucous membranes. Positive sterile site cultures include deep visceral and musculoskeletal abscesses obtained in a sterile manner.
- Development of any new antibiotic drug resistance in *S. aureus* until day 90. This includes any new resistance absent in the *S. aureus* from the initial blood culture and detected in any *S. aureus* cultured after the start of the intervention.
- Days alive and free of antibiotics up to day 90
- At hospital discharge, the number of days a patient received antibiotics will be recorded. At day 90, an additional check will be conducted in case additional antibiotics were prescribed after hospital discharge.

Patient-reported outcomes:

SF-36 questionnaire:¹⁰⁵⁻¹⁰⁷ This represents a validated patient-reported outcome measure and will give more detailed information of the patient's physical, mental, emotional, and social well-being. Participants will receive this questionnaire on day 90 after randomisation either via mail or E-mail (based on participant preference). The questionnaire will be available in German, English, French, and Italian. From the SF-36, the following two outcome measures are derived:

- Physical health at day 90 (measured with the SF-36 questionnaire, Mental Component Summary)
- Mental health at day 90 (measured with the SF-36 questionnaire, Physical Component Summary)

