9. STUDY ASSESSMENTS

9.1 Study flow chart/ table of study procedures and assessments

Study Schedule

	Screening	Enrolment	Intervention phase					In-Hospital Follow-Up (applicable only if participant remains hospitalised)				Close-out
Time point	0-72h before randomisation		Day 1	Day 2	Day 3	Day 4	Day 5	Day 7	Day 14	Day 28	Discharge day	Day 90
S. aureus positive blood culture	X											
Identification of patient		X										
Eligibility checks		X										
Informed consent		X										
Randomisation			X									
IMP administration			X	X	X	X	X					
Time point	0-72h before randomisation		Day 1 (-1 day)	Day 2	Day 3 (±1 day)	Day 4	Day 5 (±1 day)	Day 7 (±1 day)	Day 14 (±3 days)	Day 28 (±4 days)	Discharge day	Day 90 (±7 days)
Clinical assessments												
Baseline data			X ¹									
SIRS criteria								X				
All-cause mortality								Assessed until day 90				
Clinical failure										X	X	X
Length of hospital stay											X	
Length of ICU stay											X	
Antibiotic and/or surgical treatment												X
Laboratory assessments												
Blood cultures				X			X ²					
Creatinine			X				X			X ³		
CRP			X				X					
ALT and gGT			X				X			X ³		
Blood count (Hb, Tc, Lc)			X		X		X	X				
Linezolid trough conc.							X ⁴					
Microbiological failure										X	X	X
New antibiotic resistance												X
Patient reported outcomes												
Quality of life (SF-36)												X
Return to usual level of function												X
Safety assessments												
Serotonin toxicity, myelosuppression, hyperlactataemia ⁵			X	X	X	X	X	X				
Acute kidney injury ⁵							X		X			
C. difficile-associated diarrhoea ⁵												X
SAE / SAR			Collected until day 90									

Abbreviations: S. aureus – *Staphylococcus aureus*; SAE – Severe Adverse Event; SAR – Severe Adverse Reaction; SIRS - Systemic Inflammatory Response Syndrome; ICU – Intensive Care Unit; CRP – C-Reactive Protein; ALT – Alanine Transaminase; gGT – Gamma-glutamyl Transferase; Hb – Haemoglobin; Tc – Thrombocytes; Lc – Leukocytes; SF-36 – Short Form-36

¹ Baseline data include: date of hospital admission, index blood culture, linezolid susceptibility, ethnicity, vital signs, comorbidities, standard antibiotic treatment, markers of severity (mechanical ventilation, cardiac arrest, use of vasopressors, ICU), injection drug use, mental health diagnosis.

² Assessment of persistent bacteraemia. Only required if day 2 blood culture is positive or recorded if done as part of standard of care.

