9.3.8 Follow-up blood cultures (day 2, day 5 ± 1)

Follow-up blood cultures are routinely performed and repeated in *S. aureus* bacteraemia until blood cultures become negative. This belongs to the guidelines-supported management of such infections. At day 2 after trial enrolment one further pair of blood culture should be drawn. This needs to be ordered by the treating physician. If the prior blood cultures were still positive for *S. aureus*, then these follow-up blood cultures will be routinely ordered and drawn. If the prior blood cultures were negative, then the blood cultures at day 2 need to be ordered additionally to the clinical routine. If day 2 blood culture stayed positive, then further follow-up cultures are mandated at day 5 (± 1) and will be part of the clinical routine as outlined above.

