11.4.3 Secondary Analyses

We intend to conduct the following analyses for the secondary outcomes:

Logistic regression

- Returning to usual level of function by day 90
- Microbiological treatment failure 14-90 days after randomisation
- Early microbiological treatment failure 5-13 days after randomisation
- Clinical treatment failure 14-90 days after randomisation
- Persistent bacteraemia defined as positive blood culture on day 5 after randomisation
- Meeting two or more SIRS criteria simultaneously on day 5 after randomisation

Log-normal linear regression

- Length of hospital stay of acute index inpatient hospitalisation (in days)

Poisson regression

- Number of days without being on the Intensive Care Unit (ICU) up to day 90
- Number of days alive and free of antibiotics up to day 90

Cox proportional hazards model

- Time to death up to day 90

Fine & Gray competing risk model

- Time to being discharged alive (assessed until day 90)

The models listed above will include sex, ICU stay at baseline, and centre as adjustment factors (will be further pre-specified in separate data analysis plan).

Wilcoxon-Mann-Whitney test

- Physical health at day 90 as assessed by the short form 36 (SF-36) questionnaire
- Mental health at day 90 as assessed by the short form 36 (SF-36) questionnaire

Subgroup analyses: We will conduct the following subgroup analyses on the primary outcome to assess if treatment effects differ by sex (male vs. female), ICU status at baseline (participants on ICU vs. participants not on ICU), and dominant focus of infection (vascular catheter, skin and soft tissue, endocarditis, osteoarticular, pneumonia, other focus, or focus not identified).

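### The assumed-negative rule for a missing day-5 blood culture lets a day-2 negative override a later day-3 positive, and leaves last-positive participants without a day-5 culture to drop out

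*Protocol*

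**What the plan says.** Protocol section 9.2.2 defines the outcome as "Persistent bacteraemia: positive blood culture on day 5 (± 1 day) after randomisation", so a culture on day 4, 5 or 6 counts directly. For a participant with no such culture it adds: "If blood culture on day 2 or 3 is negative, then day 5 blood culture will be assumed to be negative (in case it is" (the sentence closes by limiting this to cultures that were never taken). It gives no rule for an earlier positive.

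Three other places bear on this:

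- Section 9.3.8 plans a day-2 culture for everyone ("At day 2 after trial enrolment one further pair of blood culture should be drawn") and adds: "If day 2 blood culture stayed positive, then further follow-up cultures are mandated at day 5", with a window of one day either side. It also describes routine care as repeating cultures in *S. aureus* "bacteraemia until blood cultures become negative".
- Section 9.1, footnote 2, says of the day-5 culture: "Only required if day 2 blood culture is positive or recorded if done as part of standard of care". The schedule contains no day-3 culture.
- Section 11.4.3 analyses the outcome by logistic regression. Section 11.5 considers multiple imputation for secondary outcomes only when more than 5% of participants are excluded, and leaves the imputation strategy for each outcome to the separate analysis plan.

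**The concern.** Two features of the rule push the reported proportion downwards.

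First, the 'or' ignores the order of the results. One negative on day 2 is enough, whatever day 3 showed. The only required day-5 culture depends on day 2, so a participant who turns positive on day 3 has no protocol-mandated culture to correct the record.

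Second, the rule keeps negatives and leaves positives open. A day-2 negative who dies on day 3 is retained as not persistent. A day-2 positive who dies on day 3, or whose mandated draw is missed, has no value and leaves the regression. The participants lost are then nearly all from the group in which persistence occurs.

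At stake is the absolute proportion with persistent bacteraemia. If early death or missed draws differed between arms, the comparison would be affected as well.

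**Working it through.** The protocol states no rate of positive follow-up cultures, no rate of missing day-5 cultures and no power for this outcome, so there is no figure to reproduce. The check has two parts: the rule applied to each culture pattern, then an illustration on assumed rates.

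**1. Patterns when no culture was taken on days 4 to 6**

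| Day 2 | Day 3 | Day-5 culture mandated? | Value under 9.2.2 | Latest result |
|---|---|---|---|---|
| negative | negative or not done | no | negative | negative |
| positive | negative | yes | negative | negative |
| positive | positive or not done | yes | none (missing) | positive |
| negative | positive | no | **negative** | **positive** |

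Only the last row contradicts its own latest result. The third row is missing, not negative.

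**2. Size of the 'or' problem**

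The assumed inputs are:

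- share positive on day 2, p2 = 20–30%;
- chance of a day-3 positive after a day-2 negative, s = 1–5%;
- chance of no culture on days 4 to 6 after that, u = 5–50%;
- chance of being truly positive on day 5, r = 50%.

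The number wrongly called negative is 606 × (1 − p2) × s × u × r.

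- Low end: 606 × 0.70 × 0.01 × 0.05 × 0.5 = 0.11.
- High end: 606 × 0.80 × 0.05 × 0.50 × 0.5 = 6.06.

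**3. Size of the missing-positive problem**

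Let m be the share of day-2 positives with no day-5 culture, and q the share of day-2 positives still positive on day 5. Suppose first that the missing resemble the observed.

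- True proportion = p2 × q.
- Complete-case proportion = p2 × (1 − m) × q / (1 − p2 × m).

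With q = 50% assumed:

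- m = 0 (mandate fully met): no error.
- p2 = 30%, m = 10%: 0.30 × 0.90 × 0.50 / (1 − 0.03) = 13.9%, against 15.0% true, which is 7% too low in relative terms.
- Over p2 = 10–40% and m = 5–20%: 3% to 18% too low.

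**4. Effect on the odds ratio**

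Assume day-2 positivity of 24% with linezolid and 30% with placebo, and q = 50%. The true odds ratio is (0.12/0.88) / (0.15/0.85) = 0.773. With m = 10% in both arms it becomes 0.770.

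Unequal missingness does more. With p2 = 30% and q = 50% in both arms, m = 5% in one arm gives 14.5% and m = 15% in the other gives 13.4%. A true odds ratio of 1.00 then reads as about 1.10, with the more completely sampled arm looking worse.

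**5. Would carrying positives forward be better?**

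Take p2 = 25%, m = 10% and 30% of day-2 positives still positive on day 5, in the missing as in the observed. The true proportion is 0.25 × 0.30 = 7.5%.

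- Present rule: 0.25 × 0.90 × 0.30 / (1 − 0.025) = 6.9%, an error of −7.7%.
- Every last positive counted as persistent: 0.25 × (0.90 × 0.30 + 0.10) = 9.25%, an error of +23%.

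If instead 60% of the missing are truly persistent, the true value is 0.25 × (0.90 × 0.30 + 0.10 × 0.60) = 8.25%, and the errors are −16% and +12%. Carry-forward wins only if the missing are much worse than the observed.

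**6. The 5% threshold**

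The share excluded is p2 × m. At p2 = 25% it is 2.5% for m = 10% and 5.0% for m = 20%. Neither exceeds 5%, so the imputation in section 11.5 need not be triggered.

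**The case against.** The asymmetry has a reason. A positive day-2 culture makes the day-5 culture mandatory, with a three-day window, so only day-2 negatives routinely need an assumed value. If the mandate is met, the second problem vanishes apart from deaths before the window. Early discharge adds little: sections 8.2.1 and 8.9 call it unlikely or rare before day 5. A last-positive participant without a day-5 culture is missing, not negative, and section 11.5 leaves imputation to the analysis plan. The day-3 positive pattern is held down by routine repetition of cultures, and any culture on days 4 to 6 counts directly.

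Most of this stands, and it limits the point. It does not repair the 'or', which this protocol fixes and no other section corrects. Nor does it cover participants who die before day 4, whom a mandate cannot reach: day-2 negatives among them are kept and day-2 positives are not.

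A reader might infer that persistent bacteraemia *is* undercounted, or that the treatment comparison is biased. The documents support neither. Every rate above is an assumption, and the odds ratio shifts materially only if missingness among day-2 positives differs between arms, for which the protocol gives no evidence. A reader might also infer that positives should simply be carried forward. Step 5 shows that this can overcount by more than the present rule undercounts.

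**Conclusion.** The rule as worded gives a wrong value in one identifiable pattern: day 2 negative, day 3 positive, nothing on days 4 to 6. That follows from the text and needs no assumption. Its frequency is probably low, about 0.1 to 6 of 606 on the assumed ranges.

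The unequal treatment of last-negative and last-positive participants can make the reported proportion somewhat too low: zero if every mandated draw is obtained, and 3% to 18% in relative terms if 5% to 20% of day-2 positives lack one and resemble the rest. The true size cannot be known from the protocol. This is a minor point on one secondary outcome; the primary DOOR analysis does not use the day-5 result.

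**What to change.** Replace the sentence in section 9.2.2 with: *If no blood culture is taken on day 5 (±1), the result is assumed negative only if the most recent blood culture from day 2 onwards and before this window is negative.*

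In the analysis plan, treat a participant whose last culture was positive and who has no day-5 (±1) culture as missing. Impute the value using the day-2 and day-3 results, whether or not the 5% threshold in section 11.5 is passed. Add one sensitivity analysis that counts all such participants, including early deaths, as persistent. Do not make that the main rule.

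The cost is one amended sentence and slightly more analysis work, with no new cultures or visits. The change should be made before unblinding.

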Rank	Alive at 90 days	Return to usual level of function by day 90	None of the following complications:	Hospital length of stay																								
1	Yes	Yes	Yes (no complications occurred)	Ties will be resolved using the length of hospitalisation																								
2	Yes	Yes	No (complication occurred)																									
3	Yes	No	Yes (no complications occurred)																									
4	Yes	No	No (complication occurred)																									
5	No	Not applicable	Not applicable	Not applicable																								

Table 1: Desirability of Outcome Ranking (DOOR) outcome used for the LIPS trial

Secondary outcomes:

Day of randomisation is defined as day 1.

- All-cause mortality at 90 days
- Time to death up to day 90
- Proportion of participants back to their usual level of function at day 90
- Microbiological failure at 14-90 days leading to treatment change
- Early microbiological failure at 5-13 days leading to treatment change
- Clinical failure at 14-90 days leading to treatment change
- Early clinical failure at 5-13 days leading to treatment change
- Hospital length of stay after randomisation
- Time to being discharged alive (assessed by day 90)
- Number of days without being on the Intensive Care Unit (ICU) up to day 90
- Number of days alive and free of antibiotics up to day 90
- Mental health at day 90 (SF-36 questionnaire)
- Physical health at day 90 (SF-36 questionnaire)

	
 Persistent bacteraemia: S. aureus-positive blood culture on day 5 ≥ 2 systemic inflammatory response syndrome (SIRS) criteria on day 5 Change in C-reactive protein on day 5 Development of new antibiotic drug resistance in Staphylococcus aureus 
Adverse events/safety:
 
 Serious adverse reactions until day 90 Adverse events leading to study drug discontinuation Adverse events of special interest: clinical signs of serotonin toxicity, laboratory signs of myelosuppression, hyperlactataemia, acute kidney injury, Clostridioides difficile-associated diarrhoea within 90 days
Study design:	Multi-centric, 1:1 randomised, parallel group, placebo-controlled clinical trial with blinded participants, physicians, and outcome assessors conducted in the acute-care hospital setting.

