5.2 Secondary Outcomes

The secondary outcomes include each part of the DOOR outcome separately as well as additional patient-relevant outcomes and specific outcomes of interest to assess the influence on infection dynamic and control. The secondary outcomes have been aligned to the SNAP trial to allow comparison of the data at a later time point.

Separate parts of the DOOR outcome:

- All-cause mortality at 90 days
- Return to usual level of function at day 90
- Microbiological treatment failure 14-90 days after randomisation leading to treatment change
- Clinical treatment failure 14 and 90 days after randomisation leading to treatment change
- Length of hospital stay of acute index hospitalisation
- Adverse events leading to study drug discontinuation

Clinical outcomes:

- Time to death up to day 90
- Time to being discharged alive
- Number of days without being on the ICU up to day 90

Infection dynamics and control:

- Persistent bacteraemia: positive blood culture on day 5 (± 1 day) after randomisation
- Two or more systemic inflammatory response syndrome (SIRS) criteria on day 5 after randomisation
- Change in C-reactive protein (CRP) from day 1 until day 5 (± 1 day) after randomisation
- Early microbiological treatment failure 5-13 days after randomisation leading to treatment change
- Early clinical treatment failure 5-13 days after randomisation leading to treatment change

- Development of any new antibiotic drug resistance in *S. aureus* until day 90
- Number of days alive and free of antibiotics in the 90 days

Patient-reported outcomes:

- Physical health at day 90 as assessed by the short form 36 (SF-36) questionnaire.¹⁰⁵⁻¹⁰⁷
- Mental health at day 90 as assessed by the short form 36 (SF-36) questionnaire.¹⁰⁵⁻¹⁰⁷

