9.3.14 Assessment of microbiological failure (day 28, discharge day, day 90 ±7)

“Early microbiological failure” and “microbiological failure” are defined as the identification of any new focus of *S. aureus* between 5 and 13 days, or 14 and 90 days after randomisation, respectively. This will be assessed by reviewing the participant’s microbiological results in the electronic health records. Any detection of *S. aureus* (by culture or by culture-independent methods such PCR) within the time frame will be further investigated in detail by reviewing the corresponding clinical health records. Thereby it can be determined – if necessary - whether the *S. aureus* originated from a sterile site. Any change of the initial antibiotic (and/or surgical) treatment plan will be analysed if it occurred due to proven detection of *S. aureus* at a sterile site. During the 90-day telephone call, it will be asked if any microbiological samples were taken outside of the corresponding centre. If this is the case, the responsible laboratory will be directly contacted to ask to provide the corresponding results. The principal investigator of each site will finally decide if a microbiological failure occurred. Furthermore, the independent outcome assessment board will review each documented microbiological failure on a case-by-case basis.

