9.3.15 Assessment of clinical failure (day 14, day 28, discharge day, day 90)

“Early clinical failure” and “clinical failure” are defined as the identification of any new focus of *S. aureus* between 5 and 13 days, or 14 and 90 days after randomisation, respectively. This encompasses not only microbiological findings (i.e. detection of *S. aureus*) but also clinical, radiological and histological results. Clinical failure will be assessed by screening of patient history on multiple levels in the available electronic health records and during the telephone call at day 90: any change of the initial antibiotic (and/or surgical) treatment plan will be analysed if it occurred due to proven or assumed new focus of *S. aureus*. Further, all available microbiological results, histological results as well as radiological exams will be screened for signs of newly identified *S. aureus* focus/foci. In case of ambiguous interpretations, the treating physicians can be contacted directly to inquire his/her interpretation of the results. The principal investigator of each site will finally decide if a clinical failure occurred. Furthermore, a blinded panel of experts, selected by the trial investigators, will review each documented clinical failure on a case-by-case basis.

9.3.16 Assessment of length of hospital stay and length of ICU stay (discharge day)

At the time of acute care hospital discharge, the length of hospital stay will be documented according to the hospital records. Similarly, length of stay on the ICU will be extracted from the electronic hospital records.

9.3.17 Assessment of all-cause mortality (day 7, day 14, day 28, day 90 ±7)

The data will be examined in both the hospital records and, when available, external documents to ascertain whether the participant has died during the follow-up period. If the participant cannot be reached for the 90-day telephone follow-up, their emergency contact or primary care physician will be contacted. Documentation of the presumed cause of death is not mandatory.

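### Section 9 misstates three outcome definitions: the SF-36 component summaries are crossed, early clinical failure is given days 14–90, and 9.3.14 opens by defining microbiological failure as a new focus

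*Protocol*

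**What the plan says.** **SF-36.** Protocol 9.2.2 derives two measures from the questionnaire: "Physical health at day 90 (measured with the SF-36 questionnaire, Mental Component Summary") and "Mental health at day 90 (measured with the SF-36 questionnaire, Physical Component Summary"). The analysis list in 11.4.3 says only "Physical health at day 90 as assessed by the short form 36 (SF-36) questionnaire", and likewise for mental health. The synopsis, 5.2 and 9.3.19 name no component summary either.

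**Early clinical failure.** The synopsis lists "Early clinical failure at 5-13 days leading to treatment change", and 5.2 lists "Early clinical treatment failure 5-13 days after randomisation leading to treatment change". Section 9.3.15 uses the same window. The entry in 9.2.2 carries days 5–13 in its name, but the sentence that defines it reads "Newly identified focus of *S. aureus* between 14 and 90 days after randomisation as determined by the site investigator".

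**Microbiological failure.** Sections 5.1 and 9.2.1 (days 14–90) and 9.2.2 (days 5–13) define it as any positive sterile-site culture with S. aureus. Section 9.3.14 opens differently: early and late microbiological failure "are defined as the identification of any new focus of *S. aureus* between 5 and 13 days", or 14 and 90 days for the late outcome. Section 9.3.15 uses the same wording for clinical failure and then adds "This encompasses not only microbiological findings (i.e. detection of *S. aureus*) but also clinical, radiological and histological results". After its first sentence, 9.3.14 has every detection of S. aureus in the window (by culture, or by a culture-independent method such as PCR) investigated for sterile-site origin.

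**The concern.** These are the sentences that tell sites and analysts what each outcome is.

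- **SF-36.** Followed literally, each result is reported under the other's name. The data are intact, but 9.2.2 is the only place where the protocol fixes the score.
- **Early clinical failure.** Followed literally, either no event can qualify or the outcome repeats late clinical failure.
- **Microbiological failure.** Late microbiological failure leading to treatment change is part of the DOOR complications domain, which separates rank 1 from 2 and rank 3 from 4. Clinical failure already requires a newly identified focus, so a persistent or relapsing culture at a known site enters the failure component only as microbiological failure. The opening sentence of 9.3.14 closes that route. Section 5.1 justifies the domain by persistent and relapsing as well as new infection, and the synopsis by persistence or spread, so the sentence also conflicts with the protocol's own rationale.

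**Working it through.** **Definitions side by side**

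| Outcome | Stated in the passage at fault | Stated elsewhere |
|---|---|---|
| Physical health (SF-36) | Mental Component Summary (9.2.2) | no score named (synopsis, 5.2, 9.3.19, 11.4.3) |
| Mental health (SF-36) | Physical Component Summary (9.2.2) | no score named (same sections) |
| Early clinical failure | days 14–90 (9.2.2, defining sentence) | days 5–13 (9.2.2 outcome name, synopsis, 5.2, 9.3.15) |
| Microbiological failure | any new focus (9.3.14, first sentence) | any positive sterile-site culture (5.1, 9.2.1, 9.2.2) |

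Days 5–13 are 9 days and days 14–90 are 77 days; they share none. The 14–90 sentence matches the wording for late clinical failure in 9.2.1, item b.

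**Size of the third item.** The protocol gives no frequency of same-site culture failure, so the count is assumed.

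Inputs from 11.2 (control v linezolid): death 22.5% v 20.3%; worse function 25.0% v 21.3%; complications 6.3% v 5.0%; 550 participants, hence 275 per arm. Assumptions: the function and complication rates apply to survivors, components are independent, and no data are missing.

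1. Both alive: 0.775 × 0.797 = 0.618.
2. Same function status: 0.75 × 0.787 + 0.25 × 0.213 = 0.6435.
3. Pairs reaching the complications tier: 0.618 × 0.6435 = 0.397.
4. Pairs decided there: 0.397 × (0.063 × 0.950 + 0.937 × 0.050) = 0.0424.

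Share of all pairs that reach the tier through one given survivor:

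- control, function returned: 0.797 × 0.787 / 275 = 0.228%; not returned: 0.797 × 0.213 / 275 = 0.062%
- linezolid, function returned: 0.775 × 0.75 / 275 = 0.211%; not returned: 0.775 × 0.25 / 275 = 0.070%
- averages: control 0.186%, linezolid 0.181%

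With 1, 3 or 5 unrecorded survivors in each arm, at most 0.37%, 1.10% or 1.84% of pairs are affected.

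**Win ratio.** Shares of pairs won v lost by linezolid:

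- mortality 0.1793 v 0.1573
- function 0.1215 v 0.0987
- complications 0.0238 v 0.0186
- sums 0.3246 v 0.2746, leaving 0.3551 to length of stay, won by linezolid with assumed probability p

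WR = (0.3246 + 0.3551p) / (0.2746 + 0.3551(1 − p)).

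If a control and b linezolid survivors go unrecorded, the complication rates become 0.063 − a/(275 × 0.775) and 0.050 − b/(275 × 0.797). With a = b = 5 these are 0.0395 and 0.0272. Wins before length of stay are then 0.3161, losses 0.2664, and 0.3718 goes to length of stay. At p = 0.65, WR = (0.3161 + 0.2417) / (0.2664 + 0.1301) = 1.407.

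| p | Base WR | Shift, 5 v 5 | Shift, 5 control v 1 linezolid | Shift, 1 control v 5 linezolid |
|---|---|---|---|---|
| 0.50 | 1.1106 | −0.0006 | −0.017 | +0.017 |
| 0.60 | 1.2905 | +0.0085 | −0.015 | +0.025 |
| 0.65 | 1.3924 | +0.0144 | −0.013 | +0.031 |

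Over all counts from 1 to 5 per arm at these values of p, the shift runs from −0.017 to +0.031.

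For scale, survivors with any complication at the planned rates number 275 × 0.775 × 0.063 = 13.4 (control) and 275 × 0.797 × 0.050 = 11.0 (linezolid). Five per arm would be 37% and 46% of them, so 5 is a generous upper end.

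**The case against.** The first two slips are easy to recognise. A swap between two adjacent lines is unlikely to survive scoring, and the right window for early clinical failure stands in the same entry and in three other sections. Both points are fair, and they are why these items are minor.

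On the third, the conflict is one sentence. Nothing later in 9.3.14 requires a new focus: the rest of the section asks whether the organism came from a sterile site. Three other sections agree on the definition, and under 1.3 the outcome board overrules sites. That largely stands. What remains is that 9.3.14 leaves the final decision to the site's principal investigator and has the board review documented failures, so a case that a site never documents may not reach it.

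A reader might infer three stronger things that the documents do not support:

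- **That up to 4.2% of pairs are at risk.** That is the whole complications tier. It also holds clinical failure, serious adverse reactions and adverse events leading to study drug discontinuation, none of which 9.3.14 removes.
- **That blinding keeps the shift below 0.015.** Blinding makes the recording rule the same in both arms, not the number of omitted events. The plan itself expects 6.3% v 5.0% complications, so the smaller bound needs equal counts as a stated assumption.
- **That PCR-only detection must be excluded.** Section 9.3.14 lists PCR expressly and the other sections speak of culture. The documents leave the question open.

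**Conclusion.** All three misstatements are in the current text and should be corrected. Items 1 and 2 concern secondary outcomes only; no data are lost, and the intended window for early clinical failure can be recovered from other sections. Item 3 reaches a component of the primary outcome, but only for a survivor whose sole complication is a same-site positive culture on days 14–90 leading to treatment change, at a site that applies the opening sentence over the rest of its own section.

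Its effect on the win ratio is probably small: under 0.015 with equal counts per arm and up to about 0.03 with unequal counts. Those limits rest on the assumed 1 to 5 unrecorded survivors per arm, a length-of-stay win probability of 0.50 to 0.65, and the independence and no-missing-data simplifications. Nothing here shows a systematic bias between arms or changes the planned sample size, power or significance level. This is a minor consistency correction of outcome definitions; no analysis choice is at issue.

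**What to change.** In a protocol amendment:

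1. In 9.2.2, swap the SF-36 labels: Physical Component Summary for physical health, Mental Component Summary for mental health.
2. In 9.2.2, put days 5–13 in the defining sentence for early clinical failure.
3. Replace the opening sentence of 9.3.14 with the sterile-site-culture definition of 5.1, 9.2.1 and 9.2.2, days 5–13 for early and 14–90 for late failure. Carry the treatment-change condition as those sections state it.
4. Reconcile the mention of PCR in 9.3.14 with the culture wording elsewhere by stating whether PCR-only detection counts.
5. Check that the eCRF and the site instructions use the same definitions.

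The cost is a few sentences and one cross-check, with no burden on participants and no loss of data. It is best done before failures are adjudicated and the analysis plan is finalised, so that the corrections cannot look post hoc.
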